2.7.4 SUB-SET OF PARTICIPANTS THAT ELECT TO UNDERGO LYMPH NODE BIOPSY

Between each adjuvant group, compare the magnitude and frequency of HIV-1-specific TfH cells in total lymph nodes and lymph node follicles, TfH and B cell distribution between intra and extrafollicular LN zones, and levels of cellular activation using ICS, immunohistochemistry, transcriptional analyses, and related techniques at weeks 14 and 58.

3 INVESTIGATIONAL PRODUCTS

3.1 DESCRIPTION OF STUDY AGENTS

3.1.1 ENV-C PLASMID DNA VACCINE

The Env-C Plasmid DNA vaccine is supplied as single-dose vials containing 0.9 mL of solution at a concentration of 4 mg/mL. Each 1 mL of solution contains 4 mg of Env DNA vaccine and 9 mg of sodium chloride. The Env DNA vaccine will be stored at $\leq -60^{\circ}\text{C}$ and shipped on dry ice to the clinical research site. When thawed, the study product appears as a clear, colorless liquid.

3.1.2 HIV-1 ENV GP145 C.6980

The HIV Env gp145 C.6980 protein vaccine is supplied as single-dose vials containing 0.7 mL of solution at a concentration of 600 $\mu\text{g}/\text{mL}$. The buffer is PBS, pH 7.4. The HIV Env gp145 C.6980 protein vaccine will be stored at $\leq -65^{\circ}\text{C}$ and shipped on dry ice to the clinical research site. When thawed, the study product appears as a clear, colorless liquid.

3.1.3 RECOMBINANT DOUBLE MUTANT ESCHERICHIA COLI HEAT-LABILE TOXIN LT (R192G/L211A) (dmLT)

The dmLT adjuvant will be supplied as a multiple-dose vial (up to two doses can be withdrawn from a vial) containing 0.5 mg of lyophilized product. The lyophilized product was formulated at 1 mg/mL in phosphate-buffered saline containing lactose, pH 7.4 and appears as a solid cake, consistent, and white to off-white. Each vial of dmLT will be reconstituted with 0.5 mL of sterile water for injection, resulting in a concentration of 1 mg/mL. The reconstituted product appears as a clear, colorless solution. Filled vials were labeled for storage at $\leq -10^{\circ}\text{C}$ and are stored at $-20^{\circ}\text{C} \pm 10^{\circ}\text{C}$ prior to reconstitution. The dmLT product will be shipped to the clinical site on dry ice. After reconstitution, the dmLT product should be stored at 2-8°C for up to 12 hours. A maximum of two doses may be removed from each reconstituted vial for administration to study participants.

3.1.4 ALF43: ARMY LIPOSOME FORMULATION—43% CHOLESTEROL

The ALF43 adjuvant will be supplied as single-dose vials containing 240 μg of 3D-PHAD® per vial. ALF43 has a phospholipid to 3D-PHAD® molar ratio of 8.8 to 1. The ALF43 product appears as a white to off-white lyophilized powder, which may be in a cake at the bottom of the vial or dispersed throughout the vial. ALF43 is stored at $-20^{\circ}\text{C} \pm 10^{\circ}\text{C}$ and shipped to the clinical research site on dry ice.

3.1.5 ALUMINUM HYDROXIDE SUSPENSION—FLUID GEL (REHYDRAGEL®)

The Rehydragel® adjuvant will be supplied as 3 mL single-dose vials containing 0.7 ± 0.10 mL of aluminum suspension at a concentration of 5 ± 1 mg/mL. The vials are labeled as Aluminum Hydroxide suspension fluid gel (adjuvant). Rehydragel® appears as a white gelatinous precipitate in aqueous suspension; opaque. Rehydragel® will be stored at 2°C to 8°C and will be shipped to the clinical research site at the same temperature.

3.1.6 0.9% SODIUM CHLORIDE FOR INJECTION (STERILE SALINE)

0.9% Sodium Chloride for Injection (sterile saline) will be purchased from a commercial vendor based on availability at the time required. The sterile saline will serve as both the diluent and placebo for the trial. Sterile saline will be stored as per the manufacturer's recommendation.

Table 2: Study Agents

Short name	DP Composition	Description	Developer	Manufacturer
Env-C Plasmid DNA	DNA plasmid 3.6 mg/vial in 0.9 mL normal saline.	The Env-C Plasmid DNA drug product is a DNA plasmid vial in single-dose vials at a concentration of 4.0 mg/mL (3.6 mg/vial, 0.9 mL solution) in normal saline.	University of Massachusetts Medical School, MA	Waisman Institute, Wisconsin
HIV Env gp145 C.6980	HIV Env gp145 C.6980 0.7 mL/vial at 0.6 mg/mL in 2.7 mM potassium chloride, 136.9 mM sodium chloride, 1.5 mM potassium phosphate, and 8.9 mM sodium phosphate, pH 7.4.	The HIV Env gp145 C.6980 protein (CO6980v0c22) is vialled in PBS, pH 7.4 in single-dose vials at a concentration of 600 µg/mL with 0.7 mL/vial.	MHRP/WRAIR	ABL through Avid, Tustin, California
dmLT	500 µg dmLT in lyophilized form in sodium phosphate buffer with 5% lactose	The double mutant heat-labile enterotoxin B of E. coli , dmLT (R192G/L211A), pH 7.4 is lyophilized at 500 µg/vial (0.5 mg/vial) to be reconstituted with 0.5 mL of water for injection. After reconstitution, the buffer will be 42.7 mM sodium phosphate, 10.7 mM potassium phosphate, 82 mM sodium chloride and 5% lactose.	Tulane University	GmbH [name] Germany

ALF43	DMPC: 1.24 µmol/vial DMPG: 0.14 µmol/vial Cholesterol: 1.03 µmol/vial	Army Liposome Formulation consists of MPLA, dimyristoylphosphatidylcholine (DMPC), cholesterol (43%), and dimyristoylphosphatidylglycerol (DMPG) All of the lipids are synthetic. The MPLA congener that will be used is 3D-PHAD®. The final phospholipid concentration is 1.15 mM after reconstitution. 3D-PHAD®, is at concentration of 200 µg/mL of the 1.15 mM phospholipid liposomes after hydration	WRAIR	Avanti Polar Lipids/ WRAIR
Rehydragel® (Aluminum hydroxide suspension--fluid gel)	5 mg/mL aluminum in H ₂ O	Rehydragel® was vialed at 0.7 mL ± 0.10 mL volume; aluminum concentration of 5 ± 1mg/mL	ChemTrade New Jersey	VRC Pilot Plant, NIAID, NIH

See IB for details for individual vaccine component details.

3.2 ACQUISITION AND DISTRIBUTION

Distributed through NIAID Clinical Research Products Management Center (CRPMC)

- Env-C Plasmid DNA (provided by HJF/MHRP)
- HIV Env gp145 C.6980 protein (provided by DAIDS/NIAID/NIH)
- ALF43 (provided by WRAIR)
- Rehydragel® (provided by the Vaccine Research Center (VRC)/NIAID/NIH)
- dmLT (provided by PATH, Division of Vaccines)
- 0.9% sodium chloride for injection will be available through the NIAID CRPMC.
- Sterile water for injection will be available through the NIAID CRPMC.

Locally sourced

- Empty sterile vials will be purchased from a commercial vendor.
- ECG skin preparation paper (Skin preparation paper) will be purchased from a commercial vendor.
- Sterile 2 x 2-inch, 12 ply cotton gauze pads, individually wrapped will be purchased from a commercial vendor.
- Nexcare™ Tegaderm™ Waterproof Transparent Dressings (3M), 4x4 ¾ inches, individually wrapped, will be purchased from a commercial vendor.

Upon successful completion of protocol registration procedures, the site pharmacist may obtain the study products made available to the study site through the NIAID CRPMC by following instructions provided in the Pharmacy Guidelines and Instructions for DAIDS Clinical Trials Networks.

3.3 DOSAGE PREPARATION, DISPENSING AND ADMINISTRATION OF STUDY PRODUCT

The vaccines will be given by intramuscular (IM) injection into the deltoid muscle, excluding the dmLT adjuvant which is given by TCI. All products will be combined into one syringe (excluding dmLT) for IM injection, i.e., Env-C Plasmid DNA and HIV Env gp145 C.6980/ALF43A for study Group 7. Once combined, the vaccine regimen must be administered as soon as possible, although based on the stability data performed in our laboratory (data not shown but a comprehensive report was provided to DAIDS), all the vaccine formulations were stable for 24 hours. This is significantly more than required time to vaccinate a participant in the clinic. Alternating deltoids will be used for subsequent immunizations [63]. Vaccination in contralateral limbs has been successfully utilized to achieve prime boost in multiple vaccine trials [63]. Alternating sites allowed for better attribution of local reactogenicity reactions.

The site for injection cleaned with an alcohol wipe before the injection. Since the interventions are vaccines, the concept of a washout period does not apply. The duration of the interventions is unknown, but it is hoped that it would be ten years or longer.

See IB and Package Inserts for further information on each study product.

126 healthy men and women between the ages of 18 and 40 years will be randomized to one of seven groups:

Table 3: Study Groups

Group	N V/P	Prime at weeks 0, 4, 12	Boost at weeks 20, 32, 56
1	15/3	Env-C Plasmid DNA (2 mg, IM)	HIV Env gp145 C.6980 (100 µg, IM)/Rehydragel® (500 µg, IM)
2	15/3	Env-C Plasmid DNA (2 mg, IM)	HIV Env gp145 C.6980 (100 µg, IM)/Rehydragel® (500 µg, IM) / ALF43 (200 µg, IM)
3	15/3	Env-C Plasmid DNA (2 mg, IM) + dmLT (50 µg, TCI)	HIV Env gp145 C.6980 (100 µg, IM)/Rehydragel® (500 µg, IM)
4	15/3	Env-C Plasmid DNA (2 mg, IM) + dmLT (50 µg, TCI)	HIV Env gp145 C.6980 (100 µg, IM)/Rehydragel® (500 µg, IM) / ALF43 (200 µg, IM)
5	15/3	Env-C Plasmid DNA (2 mg, IM) / ALF43 (200 µg, IM)	HIV Env gp145 C.6980 (100 µg, IM)/Rehydragel® (500 µg, IM)
6	15/3	Env-C Plasmid DNA (2 mg, IM) / ALF43 (200 µg, IM)	HIV Env gp145 C.6980 (100 µg, IM)/Rehydragel® (500 µg, IM) / ALF43 (200 µg, IM)
7	15/3	Env-C Plasmid DNA (2 mg, IM) /HIV Env gp145 C.6980 (100 µg, IM)/ALF43 (200 µg, IM)	Env-C Plasmid DNA (2 mg, IM) /HIV Env gp145 C.6980 (100 µg, IM)/ALF43 (200 µg, IM)/Rehydragel® 500 µg, IM)

IM= intramuscular, TCI = transcutaneous immunization; ALF43 (ALF43 Army Liposome Formulation with Monophosphoryl Lipid A (MPLA) and 43% Cholesterol the 3D-PHAD® dose is 200 µg); V= Vaccine Recipient; P= Placebo; Rehydragel® dose is 500 µg aluminum.

3.3.1 PREPARATION OF INVESTIGATIONAL PRODUCTS

The clinical research pharmacist will prepare all doses for administration in the pharmacy and dispense to the clinic for administration. The pharmacist must be proficient in the preparation of products requiring aseptic technique under a pharmacy biological safety cabinet/isolator. Local regulations and site institutional policies and procedures for use of protective equipment, such as gloves, gowns, face masks and safety glasses, must be followed.

To preserve blinding, the pharmacist will prepare placebo syringes in the same manner as active vaccine syringes. Upon completion of placebo syringe preparation, the pharmacist will hold the prepared syringes in the pharmacy for the same length of time as it would take to prepare and dispense active vaccine syringes. Before releasing prepared study product to the clinic, the pharmacist will place an overlay on all syringes to maintain blinding (refer to protocol sections 3.3.1 and 3.3.3)

3.3.1.1 Env-C Plasmid DNA

One vial of Env-C Plasmid DNA and 0.9% sodium chloride for injection will be needed to prepare the dose. One vial of Env-C Plasmid DNA will be removed from the -70°C or colder freezer and allowed to thaw completely at room temperature (15-30°C, approximately 15 minutes). One vial of 0.9% sodium chloride for injection will be removed from storage.

When thawed, using aseptic technique, the pharmacist will add 0.9 mL of 0.9% sodium chloride for injection to the Env-C Plasmid DNA vial using a 22-25-gauge needle and a 1-mL syringe. The diluted Env-C Plasmid DNA vial will be swirled by hand for 1-2 minutes. Using a 3-mL syringe and a 22-25 gauge needle, 1 mL of the diluted product will be withdrawn from the vial for study participant administration. The pharmacist will apply an overlay to the syringe to maintain blinding.

The syringe should be labeled as “Env-C Plasmid DNA 2 mg or Placebo 1 mL”, as well as “Administer IM in deltoid”. The study product preparation and expiration times will also be listed on the prepared participant-specific study product label. The syringe containing the study product should be bagged for transport to the clinic where it will be administered. The study product should be administered within 4 hours of preparation.

Any unused portion of vials or expired prefilled syringes should be disposed of in accordance with institutional or pharmacy policy.

3.3.1.2 Placebo for Env-C Plasmid DNA

Using aseptic technique, the pharmacist will withdraw 1 mL of 0.9% sodium chloride for injection into a 3-mL syringe. The pharmacist will apply an overlay to the syringe to maintain blinding.

The syringe should be labeled as “Env-C Plasmid DNA 2 mg or Placebo 1 mL”, as well as “Administer IM in deltoid”. The study product preparation and expiration times will also be listed on the prepared study product label. The syringe containing the study product should be bagged for transport to the clinic where it will be administered. The study product should be administered within 4 hours of preparation.

Any unused portion of entered vials or expired prefilled syringes should be disposed of in accordance with institutional or pharmacy policy.

3.3.1.3 dmLT

One vial of dmLT, cold sterile water for injection, 0.9% sodium chloride for injection, and one empty sterile vial will be needed to prepare the dose. The dmLT vial will be removed from the -20°C freezer. The sterile water for injection, the 0.9% sodium chloride for injection, and the empty sterile vial will be removed from storage and then, using aseptic technique and a 22-25-gauge needle and a 1 mL syringe, the dmLT vial will be reconstituted with 0.5 mL of cold sterile water for injection. The resulting concentration will be 1 mg/mL. The dmLT vial will be gently swirled and inverted by hand for approximately 10 times to fully suspend the contents. Following resuspension, the vial will be held at room temperature for 10-15 minutes to ensure full dissolution. The vial will be visually inspected to ensure the absence of clumps of undissolved powder. After reconstitution, a maximum of 2 doses may be removed from each reconstituted vial of dmLT for

administration to study participants. The reconstituted dmLT vial should be stored at 2-8°C for a maximum of 12 hours. Discard the reconstituted vial after this time.

Using a 22-25-gauge needle and a 3 mL syringe, 1.9 mL of cold 0.9% sodium chloride will be added to an empty sterile vial. Reconstituted dmLT will be swirled again by hand for 1-2 minutes. Then using a 0.3 mL ultra-fine insulin syringe with a 30-gauge ½-inch needle or a 0.5 mL syringe, 0.1 mL of the reconstituted dmLT solution will be withdrawn from the vial and added to the vial containing 1.9 mL of cold 0.9% sodium chloride to bring the concentration to 50 µg/mL. The vial will be swirled by hand for 1 to 2 minutes. Using a 22-25-gauge needle and a 3 mL syringe, 1 mL of the solution will be withdrawn from the vial for study participant administration.

The syringe should be labeled as “dmLT 50 µg or Placebo 1 mL”, as well as “Administer by TCI”. The study product preparation and expiration times will also be listed on the prepared study product label. The syringe containing the study product should be bagged for transport to the clinic where it will be administered. The study product must be placed in the refrigerator and removed for administration when clinic confirms participant is ready. The study product should be administered within 15 minutes of preparation. Any unused portion of vials or expired prefilled syringes should be disposed of in accordance with institutional or pharmacy policy.

3.3.1.4 Placebo for dmLT

Using aseptic technique, the pharmacist will withdraw 1 mL of 0.9% cold sodium chloride for injection, previously stored at 2 – 8 °C, into a 3 mL syringe. The syringe should be labeled as “dmLT 50 µg or Placebo 1 mL”, as well as “Administer by TCI”. The study product preparation and expiration times will also be listed on the prepared study product label. The syringe containing the study product should be bagged for transport to the clinic where it will be administered. The study product must be placed in the refrigerator and removed for administration when clinic confirms participant is ready. The study product should be administered within 15 minutes of preparation.

Any unused portion of vials or expired prefilled syringes should be disposed of in accordance with institutional or pharmacy policy.

3.3.1.5 Env-C Plasmid DNA + ALF43

One vial of Env-C Plasmid DNA, one vial of ALF43, and 0.9% sodium chloride for injection will be needed to prepare the dose. One vial of Env-C Plasmid DNA will be removed from the -70°C or colder freezer and allowed to thaw completely at room temperature (15-30°C, approximately 10-15 minutes). One vial of ALF43 will be removed from the -20°C freezer and allowed to equilibrate to room temperature (15-30°C approximately 10-15 minutes).

Once equilibrated to room temperature, using aseptic technique with a 22-25-gauge needle and a 1-mL syringe, 0.6 mL of 0.9% sodium chloride for injection will be added the ALF43 vial. The ALF43 vial will be mixed using a Vortex mixer set at 2500 RPM for 5 minutes. The vial will be incubated at room temperature for 5 minutes.

When the Env-C Plasmid DNA vial is thawed, the pharmacist will swirl by hand for 1-2 minutes. Then, using aseptic technique, the pharmacist will add 0.6 mL of Env-C Plasmid DNA to the vial containing hydrated ALF43 using a 22-25-gauge needle and a 1-mL syringe. The Env-C Plasmid

DNA + ALF43 vial will be gently swirled by hand for 1-2 minutes. Then, using a 3-ml syringe and a 22-25-gauge needle, 1 mL of the solution will be withdrawn from the vial for study participant administration.

The syringe should be labeled as “Env-C Plasmid DNA 2 mg+ALF43 200 μ g 3D-PHAD or Placebo 1 mL”, as well as “Administer IM in deltoid”. The study product preparation and expiration times will also be listed on the prepared study product label. The syringe containing study product should be bagged for transport to the clinic where it will be administered. The study product should be administered within 4 hours of preparation.

Any unused portion of vials or expired prefilled syringes should be disposed of in accordance with institutional or pharmacy policy.

3.3.1.6 Placebo for Env-C Plasmid DNA + ALF43

Using aseptic technique, the pharmacist will withdraw 1 mL of 0.9% sodium chloride for injection into a 3-mL syringe.

The syringe should be labeled as “Env-C Plasmid DNA 2 mg+ALF43 200 μ g 3D-PHAD or Placebo 1 mL”, as well as “Administer IM in deltoid.” The study product preparation and expiration times will also be listed on the prepared study product label. The syringe containing the study product should be bagged for transport to the clinic where it will be administered. The study product should be administered within 4 hours of preparation.

Any unused portion of vials or expired prefilled syringes should be disposed of in accordance with institutional or pharmacy policy.

3.3.1.7 Env-C Plasmid DNA + HIV Env gp145 C.6980 + ALF43

One vial of Env-C Plasmid DNA, one vial of ALF43, one vial of HIV Env gp145 C.6980 and 0.9% sodium chloride for injection will be needed to prepare the dose. One vial of Env-C Plasmid DNA and one vial of HIV Env gp145 C.6980 will be removed from the -70°C or colder freezer and allowed to thaw completely at room temperature (15-30°C, approximately 10-15 minutes). One vial of ALF43 will be removed from the -20°C freezer and allowed to equilibrate to room temperature (15-30°C, approximately 10-15 minutes). 0.9% sodium chloride for injection will be removed from storage. Once equilibrated to room temperature, using aseptic technique and a 22-25-gauge needle and a 1 mL syringe, 0.4 mL of 0.9% sodium chloride for injection will be added to the ALF43 vial. The hydrated ALF43 vial will be mixed using a Vortex mixer set at 2500 RPM for 5 minutes.

When the HIV Env gp145 C.6980 vial is thawed, the pharmacist will swirl by hand for 1-2 minutes. Then, using aseptic technique, the pharmacist will add 0.2 mL of the HIV Env gp145 C.6980 to the vial containing the hydrated ALF43 using a 22-25-gauge needle and a 1 mL syringe. The HIV Env gp145 C.6980 + ALF43 vial will be swirled gently with a vortex mixer set at 250 RPM for 2 minutes.

When the Env-C Plasmid DNA vial is thawed, the pharmacist will swirl by hand for 1-2 minutes. Then, using aseptic technique, the pharmacist will add 0.6 mL of Env-C Plasmid DNA to the vial containing the HIV Env gp145 C.6980 + ALF43 mixture using a 22-25-gauge needle and a 1 mL

syringe. The vial containing Env-C Plasmid DNA + HIV Env gp145 C.6980 + ALF43 will be swirled gently with a vortex mixer set at 250 RPM for 5 minutes. Using a 3-mL syringe and a 22-25-gauge needle, 1mL of this solution will be withdrawn from the vial for study participant administration.

The syringe should be labeled as “Env-C Plasmid DNA 2mg+HIV Env gp145 C.6980 100 µg +ALF3 200 µg 3D-PHAD or Placebo 1ml”, as well as “Administer IM in deltoid”. The study product preparation and expiration times will also be listed on the prepared study product label. The syringe containing the study product should be bagged for transport to the clinic where it will be administered. The study product should be administered within 4 hours of preparation.

Any unused portion of vials or expired prefilled syringes should be disposed of in accordance with institutional or pharmacy policy.

3.3.1.8 Placebo for Env-C Plasmid DNA + HIV Env gp145 C.6980 Protein + ALF43

Using aseptic technique, the pharmacist will withdraw 1 mL of 0.9% sodium chloride for injection into a 3-mL syringe.

The syringe should be labeled as “Env-C Plasmid DNA 2 mg + HIV Env gp145 C.6980 100 µg + ALF43 200 µg 3D-PHAD or Placebo 1 mL”, as well as “Administer IM in deltoid”. The study product preparation and expiration times will also be listed on the prepared study product label. The syringe containing the study product should be bagged for transport to the clinic where it will be administered. The study product should be administered within 4 hours of preparation.

Any unused portion of vials or expired prefilled syringes should be disposed of in accordance with institutional or pharmacy policy.

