3.3.3 LABELLING TO PRESERVE BLINDING

The participants, the clinical staff and the Principal Investigator will be blinded to treatment allocation. The site pharmacist will maintain the randomization code and complete assignments of participants according to the randomization allocation.

The study statistician or DCAC will prepare a randomization list for distribution via password-protected email to the pharmacist. This will include de-identified participant study numbers, treatment assignments, and randomization codes.

Site pharmacists will prepare all doses in the pharmacy and then deliver to the clinic for administration. The pharmacist will apply an overlay to the dosing syringes before applying the

syringe label to prevent possible unblinding if the appearance of the vaccines differs. The study assignment will not appear on any label or document leaving the pharmacy. The syringes will be labeled as follows:

- Participant identifier
- Study product name/placebo
- Dose and volume of all study products/placebo in the syringe
- Route (IM or TCI)
- Preparation date and time
- Expiration date and time
- Any additional information required by the jurisdiction

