5.3 ENROLLMENT AND RANDOMIZATION

There will be 18 participants per group (15 vaccine recipients and 3 placebo recipients). Investigators will be blinded to vaccine versus placebo within each group but not across groups. Participants will be block randomized. Group 1 (with a prime of Env-C Plasmid DNA IM alone at weeks 0, 4, 12) will be fully enrolled first. After the 18 participants in Group 1 are enrolled, the remaining groups, 2-7, will begin enrolling participants. Once 24 participants in Groups 2-7 have been enrolled (four from each group) and received their first vaccinations, enrollment and vaccinations in Groups 2-7 will be paused for the time it takes the PSRT to review (typically 3 to 14 days) blinded safety data from these 24 participants covering the period immediately after their first vaccination through Day 7. If it is determined to be necessary by the PSRT, the MHRP SMC will be consulted to review unblinded data to provide a recommendation on continuing enrollment.

When safety has been confirmed with PSRT review, the remaining 14 participants in each of Groups 2-7 will be enrolled, and vaccinations will continue until the first 24 participants in Groups 2-7 (four per group) have received their first boost dose (at 20 weeks—to create a time gap between boost vaccinations of the first cohort and the remaining study participants).

A second scheduled pause (this pauses boost vaccinations only; prime vaccinations can continue) will occur for Groups 2-7 after the same set of participants reviewed during the first scheduled pause (the first 24 participants (four per group) from Groups 2-7) has received its first boost (Group 1 can continue receiving vaccinations). This pause will review blinded safety data from these 24 participants, covering the period from the first boost through Day 7 after that boost. At both scheduled pauses, the PSRT will consult the SMC regarding the pause if either of the following conditions are met: 1) one (or more) participants experience an SAE that is related to a study agent, or 2) two (or more) participants experience grade 3 or 4 AEs of the same type (e.g. elevated ALT) related to a study agent. Boost vaccinations for Groups 2-7 will resume once safety data from the booster sentinel cohort have been reviewed by the PSRT and they have concluded it is safe to proceed.

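### The label texts prescribed for the Group 7 prime differ between active and placebo syringes, so labels copied verbatim could give away allocation

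*Protocol*

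**What the plan says.** Protocol 3.3.1.7 covers preparation of the active Group 7 prime and prescribes this label text: "Env-C Plasmid DNA 2mg+HIV Env gp145 C.6980 100 µg +ALF3 200 µg 3D-PHAD or Placebo 1ml". Protocol 3.3.1.8 covers the saline placebo for the same dose and prescribes: "Env-C Plasmid DNA 2 mg + HIV Env gp145 C.6980 100 µg + ALF43 200 µg 3D-PHAD or Placebo 1 mL". The active text therefore ends "3D-PHAD or Placebo 1ml" and the placebo text "3D-PHAD or Placebo 1 mL".

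The blinding rule is in 3.3.3. Participants, clinical staff and the Principal Investigator are blinded, and "The study assignment will not appear on any label or document leaving the pharmacy". The same section has the pharmacist put the overlay on the syringe first and the label afterwards.

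Section 5.3 gives the level of the blind: "Investigators will be blinded to vaccine versus placebo within each group but not across groups". It also gives the group size: "There will be 18 participants per group (15 vaccine recipients and 3 placebo recipients"). The priming schedule in Table 3 is "Prime at weeks 0, 4, 12", which is three doses.

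**The concern.** Within a group, the blind depends on a vaccine syringe and a placebo syringe looking the same to the person who handles them. The overlay hides the contents. The label has to stay readable, so its text must not differ by arm. Here the protocol prints one text under an active heading and another under a placebo heading. A pharmacist who copied each section literally would produce two versions that match allocation one to one.

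At stake is the assessment of safety in Group 7, the only group that receives DNA and protein in the same syringe. Relatedness is judged by the site investigator (8.1.8.2). Related events are part of the primary endpoint (1.2.1) and drive the pause criteria (8.3.1) and the consultation triggers at the two scheduled reviews (5.3). Four Group 7 participants are among the 24 whose blinded data feed each of those reviews.

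**Working it through.** No power or sample-size formula applies. The check is a comparison of label texts, followed by a count.

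**Product text of the label, all seven pairs in 3.3.1**

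| Product | Active / placebo section | Identical as printed | Identical ignoring spaces | Identical ignoring spaces and case |
|---|---|---|---|---|
| DNA | 3.3.1.1 / 3.3.1.2 | yes | yes | yes |
| dmLT | 3.3.1.3 / 3.3.1.4 | yes | yes | yes |
| DNA + ALF43 | 3.3.1.5 / 3.3.1.6 | yes | yes | yes |
| DNA + gp145 + ALF43 (Group 7 prime) | 3.3.1.7 / 3.3.1.8 | **no** | **no** | **no** |
| gp145 + Rehydragel | 3.3.1.9 / 3.3.1.10 | yes | yes | yes |
| gp145 + ALF43 + Rehydragel | 3.3.1.11 / 3.3.1.12 | no (one space) | yes | yes |
| DNA + gp145 + ALF43 + Rehydragel (Group 7 boost) | 3.3.1.13 / 3.3.1.14 | yes | yes | yes |

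Spaces are disregarded throughout because they can arise when a PDF is read. In the Group 7 prime pair two differences then remain: ALF3 against ALF43, and ml against mL. Ignoring case as well leaves ALF3 against ALF43.

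**Can blinded staff see the text?** Yes. By 3.3.3 the label is applied after the overlay, so the overlay does not cover it.

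**Can the text be linked to an arm?** Not from the words themselves, since both versions say that the syringe holds the product or placebo. It can be linked by someone who knows the protocol wording, where each version stands under a heading naming it active or placebo. It can also be linked by someone who notices that one version is much rarer than the other in a 15:3 group.

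**Exposure if both texts were copied verbatim**

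- Group 7: 15 + 3 = 18 participants, as the protocol states; all groups: 7 × 18 = 126, also as stated.
- Priming syringes in Group 7: 18 × 3 = 54, of which 15 × 3 = 45 are active and 3 × 3 = 9 are placebo.
- Share of planned intramuscular syringes: 54 / (126 × 6) = 54 / 756 = 7.1%.
- Share of participants: 18 / 126 = 14.3%. Share of placebo recipients: 3 / 21 = 14.3%.

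With one identical text in 3.3.1.7 and 3.3.1.8, the number of pairs that differ in characters other than spaces falls from 1 of 7 to 0 of 7, and the exposed syringes fall from 54 to 0.

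**The case against.** The strongest reply is that this is a typing slip and would never reach a syringe. The heading and mixing steps of 3.3.1.7 say ALF43, as do the product descriptions and the study tables. Section 3.3.1 tells the pharmacist to prepare placebo syringes in the same way as active ones, and 3.3.3 forbids any assignment on a label. The pharmacist who makes the labels holds the code and is charged with keeping the blind. All of this stands, and it makes verbatim copying unlikely. It does not make the two printed texts agree.

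A second reply is that a strictly literal reading proves too much. In the route line of the label, the closing full stop sits inside the quotation marks in 3.3.1.6 and 3.3.1.9 but outside in 3.3.1.5 and 3.3.1.10, so two more pairs would differ. That is fair, and such punctuation should be discounted along with spacing. What survives is a different product name and a different unit spelling in one pair only.

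Third, participants record solicited reactions themselves on a diary card, so that part of the primary endpoint does not depend on staff reading a label. This stands in part. By 8.1.1.1 the card is a memory aid, and the study record comes from the clinician's review and interview. Relatedness remains a site judgement.

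Fourth, the Group 7 boost labels are identical, so the review after the first boost could be affected only by carry-over from the prime. That stands.

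A reader might infer that allocation is revealed for all 18 participants and that the primary endpoint in Group 7 is unblinded. The protocol does not support this. It would need verbatim copying, the slip going unnoticed, and blinded staff linking a version to an arm. Nor does anything suggest that ALF3 is a separate product.

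**Conclusion.** The inconsistency is real: the active and placebo labels prescribed for the Group 7 prime do not match in product name or unit spelling, and this pair is the exception among seven. It is most likely a slip. Its consequence is conditional: if both texts were copied as printed, a visible label would follow allocation and could unblind staff in Group 7, contrary to 3.3.3. The exposure is bounded by 18 participants and 54 planned priming syringes. That figure counts planned doses and does not estimate how much unblinding would occur.

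The conclusion assumes that the text available here reproduces the protocol's characters. A reading error in the adjuvant name cannot be fully excluded, although the second character difference in the same text suggests that it was typed separately. The protocol does not show whether labels were made with or without the slip.

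**What to change.** Use one identical label text in 3.3.1.7 and 3.3.1.8, with the adjuvant named as elsewhere in the protocol and the same unit spelling in both. Check that any labels already made for this pair are identical. If two versions were in fact used, the study team needs to know before it interprets the Group 7 safety data.

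The cost is a one-line editorial correction and a label check. No dose, sample size or analysis changes.
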